# **10.1.12** Publication Policy

The site (Institution) reserves the right to publish all findings related to the project; provided, however, that Institution, Institution or Investigator shall notify Zealand Pharma of any such publication at least 30 day prior to submission for publication to allow Zealand Pharma to ensure against inadvertent disclosure of unprotected trial drug discoveries or confidential information. Zealand Pharma shall be entitled to receive in any such publication an acknowledgement of its contribution to the project. In addition, Institution, or Investigator shall delay any such publication, at the request of Zealand Pharma, for up to 90 days to permit Zealand Pharma to prepare and file one or more patent applications relating to the subject matter of such publication.

Institution shall undertake to use its best efforts to ensure that the findings of the project are made public through publications in scientific journals or scientific conferences. Institution shall undertake to use its best efforts to ensure that each publication that it seeks to publish in connection with the project complies with applicable international standards, including the requirements for financial disclosures, if applicable.

Upon Institution's publication of any findings relating to project, Zealand Pharma shall have the right to use the published information without any restrictions; provided that Zealand Pharma shall do so only with appropriate references. Upon publication Zealand Pharma shall not be liable to pay any royalties for the use or re-publication of this information.

The Sponsor will comply with the requirements for publication of trial results.

Authorship will be determined by mutual agreement and in line with International Committee of Medical Journal Editors authorship requirements.

No confidential information shall be disclosed to others without prior written consent from Sponsor. Such information shall not be used except in the performance of this trial.

# 10.2 Appendix 2: Clinical Laboratory Tests

- The analyses detailed in Table 11 will be performed at a local laboratory at the trial site.
- Samples for the safety laboratory assessments\* will be destroyed after analyzes.
- The Investigator must review all laboratory results for concomitant illnesses and AEs.

**Table 11 Laboratory Assessments** 

| Laboratory Assessments | Parameters  | Time For Assessment  |
|-------------------------------|---|--|
| Hematology*                   | 
 
Hemoglobin
 
Hematocrit
 
Red blood cell count
 
White blood cell count with Differential: 
 
Neutrophils
 
Lymphocytes
 
Monocytes
 
Eosinophils
 
Basophils
 
 
 
Platelet Count
 
  | All trial visits (screening,
Visit 1-12 and follow-up)    |
| Biochemistry*                 | 
 
Sodium
 
Potassium
 
Chloride
 
Bicarbonate
 
Blood Urea Nitrogen
 
Creatinine
 
Creatinine Clearance (estimated)
 
Glucose
 
Calcium
 
Phosphorous
 
ALP
 
ALT
 
AST
 
INR
 
Gamma-glutamyl transferase (GGT)
 
Lactic dehydrogenase
 
Conjugated bilirubin
 
Unconjugated bilirubin
 
Total bilirubin
 
Total protein
 
Albumin
 
Amylase
 
Uric acid
 
C-reactive protein
 
 | All trial visits (screening, Visit 1-12 and follow-up)       |
|                               | 
 
HbA1c
 
Cholesterol, measured orally fasting
 
Triglycerides, measured orally fasting
 
   | Visits 1, 4, 6, 9, 12 and follow-up  Visits 1, 9 and 12 only |
| Other analyses                | 
 
Magnesium
 
Zinc
 
Aldosterone
 
Citrulline
 
ADA
 
   | Visits 1, 4, 6, 9, 12 and follow-up                          |
| Urinalysis
(by dipstick)*  | 
 
PK
 
Blood
 
Glucose
 
Leukocytes
 
pH
 
  | All trial visits (screening, Visit 1-12 and follow-up)       |
| Urinalysis*                   | Protein     Sodium  | Visit 1 and 9 MBS only                                       |

|                   | 
 
Potassium
 
Calcium
 
Magnesium
 
Urea
 
Creatinine
 
  |  |
|-------------------|--|--|
| Pregnancy testing | Serum human chorionic gonadotropin (hCG) pregnancy
test (women of childbearing potential only)  | Screening and visits 1, 4, 5, 6, 7, 8, 9, 10, 11, 12 and follow-up |
| Screening tests   | 
 
FSH; as needed in women of non-childbearing potential to confirm menopause
 
HIV type 1 and 2 antibodies
 
Hepatitis B surface antigen (HBsAg)
 
Hepatitis C virus antibody (HCV)
 
 | Screening only   |

# 10.3 Appendix 3: Adverse Events: Definitions and Procedures for Recording, Evaluating, Follow-up, and Reporting

### 10.3.1 Definition of AE

### **AE Definition**

An AE is any untoward medical occurrence in a clinical trial patient administered a
medicinal (investigational or non-investigational) product and which does not
necessarily have a causal relationship with this treatment. An AE can therefore be any
unfavourable and unintended sign (including an abnormal laboratory finding),
symptom, or disease temporarily associated with the use of a product, whether or not
related to the product.

#### AEs include:

- A clinically significant worsening of a concomitant illness.
- A clinical laboratory AE: a clinical abnormality which is clinically significant, i.e., any abnormality that suggests a disease and/or organ toxicity and is of a severity that requires active management. Active management includes active treatment or further investigations, e.g., change of dose or more frequent follow-up due to the abnormality.

The following should **not** be considered as AEs:

- Pre-existing conditions, including those found as a result of screening procedures (pre-existing conditions should be reported as medical history or concomitant illness).
- Pre-planned procedure, unless the condition for which the procedure was planned has worsened from the first trial-related activity after the patient has signed the informed consent.

### **10.3.2 Definition of SAE**

If an event is not an AE per definition above, then it cannot be an SAE even if serious conditions are met (e.g., hospitalization for signs/symptoms of the disease under study, death due to progression of disease).

An SAE is defined as any untoward medical occurrence that, at any dose fulfills any of the following criteria:

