### Medical history and concomitant diseases

- 5. More than 2 SBS-related or PS-related hospitalizations (e.g., catheter-related bacteremia/sepsis, bowel obstruction, severe water-electrolytes disturbances, etc.) within 6 months prior to screening.
- 6. Poorly controlled inflammatory bowel disease (IBD) that is moderately or severely active or fistula interfering with measurements or examinations required in the trial.
- 7. Current bowel obstruction.
- 8. Known radiation enteritis or significant villous atrophy, e.g., due to active celiac disease.
- 9. Cardiac disease defined as: decompensated heart failure (New York Heart Association [NYHA] Class III-IV), unstable angina pectoris, and/or myocardial infarction within the last 6 months prior to screening.
- 10. Clinically significant abnormal electrocardiogram (ECG) as judged by the Investigator.
- 11. Human immunodeficiency virus (HIV) positive, acute liver disease including positive results for Hepatitis B antigens (HBsAg) and Hepatitis C (HCV), or unstable chronic liver disease.
- 12. Any history of colon cancer. History of any other cancers (except margin-free resected cutaneous basal or squamous cell carcinoma or adequately treated in situ cervical cancer) unless disease-free state for at least 5 years.
- 13. Hepatic impairment defined as:
  - a. Total bilirubin  $\geq 2 \times$  the upper limit of normal (ULN), or
  - b. Aspartate aminotransferase (AST)  $\geq$  5 × ULN, or
  - c. Alanine aminotransferase (ALT)  $\geq$  5× ULN
- 14. Use of GLP-1, GLP-2, human growth hormone (HGH), somatostatin, or analogs thereof, within 3 months prior to screening.
- 15. Known or suspected hypersensitivity to glepaglutide, its components or related products.
- 16. Use of dipeptidyl peptidase (DPP)-4 inhibitors within 3 months prior to screening.
- 17. Surgical resection of gut tissue within 6 months prior to screening.
- 18. Systemic immunosuppressive therapy for treatment of the gastrointestinal tract that has been introduced or has been unstable within 3 months prior to screening.
- 19. Unstable biological therapy (e.g. anti-TNF-α, natalizumab, etc.) within 6 months prior to screening, including significant changes in doses or switch of drug.

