### **10.1.6** Committees Structure

# **Internal Safety Committee**

An internal Sponsor Safety Committee is constituted to perform ongoing safety surveillance of clinical trials with glepaglutide, including this trial.

If safety signals or concerns are observed, whether based on reported SAEs, review of all AEs and laboratory parameters reported or any other notification of significant findings, the Safety Committee will respond appropriately to protect the safety of the patients.

The Safety Committee meets quarterly and additionally on an ad-hoc basis, as needed, and will call upon external expertise when judged needed.

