# c. Requires inpatient hospitalization or prolongation of existing hospitalization

- In general, hospitalization signifies that the patient has been detained (usually involving at least an overnight stay) at the hospital or emergency ward for observation and/or treatment that would not have been appropriate in the physician's office or outpatient setting. Complications that occur during hospitalization are AEs. If a complication prolongs hospitalization or fulfills any other serious criteria, the event is serious. When in doubt as to whether "hospitalization" occurred or was necessary, the AE should be considered serious.
- Hospitalization for elective treatment of a pre-existing condition that did not worsen from baseline is not considered an AE.

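### The disease-related examples in the SAE definition contradict the protocol's own AE definition, so a site could leave SBS-related admissions or deaths out of safety reporting

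*Protocol*

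**What the plan says.** Protocol section 10.3.2 opens with a conditional rule: if an event falls outside the AE definition that precedes it, "then it cannot be an SAE even if serious conditions are met (e.g., hospitalization for signs/symptoms of the disease under study". In full, the parenthesis gives two examples: "hospitalization for signs/symptoms of the disease under study, death due to progression of disease".

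The definition it points back to is in section 10.3.1: "An AE is any untoward medical occurrence in a clinical trial patient" who is given a medicinal product, whether or not the product caused it. That section counts clinically significant worsening of a concomitant illness as an AE. It takes out only pre-existing conditions and pre-planned procedures whose underlying condition has not worsened.

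Criterion c of section 10.3.2 has one exemption for admissions: "Hospitalization for elective treatment of a pre-existing condition that did not worsen from baseline is not considered an AE". Criterion a lists death with no exception. The outcome categories in section 10.3.3 require an AE with a fatal outcome to be reported as an SAE.

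Two other places bear on which admissions could be taken for signs of the disease. Exclusion criterion 5 in section 5.2 uses the label "SBS-related or PS-related hospitalizations (e.g., catheter-related bacteremia/sepsis, bowel obstruction, severe water-electrolytes disturbances, etc". The background in section 2.2 describes dehydration as a possible result of untreated malabsorption.

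**The concern.** A site with a patient admitted for dehydration finds two answers in the same appendix. Section 10.3.1 makes the admission an AE, and criterion c then makes it serious. The parenthesis in 10.3.2 offers the same kind of admission as an example of something that is not an AE at all.

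Treatment-emergent AEs are a safety endpoint of the trial, and SAP section 4.4 tabulates treatment-emergent SAEs as sites classify them. PS is adjusted by an algorithm at each visit (protocol sections 4.1 and 8.2.9), and section 4.2 says that the long-term effects of reduced PS on the body are unknown. A fluid-related admission could therefore reflect the intervention and yet look like the underlying disease. With a single arm, no control rate would expose under-reporting, and section 9.6 provides no DMC.

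**Working it through.** The plan gives no figure on this point, so the check is mainly textual.

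**1. Does the opening condition settle the matter?** The rule bars only events that fail the AE definition. Read alone, it is harmless. But the parenthesis lists events that meet a seriousness criterion and yet are supposed not to be AEs, so it tells the reader how the condition resolves for disease-related admissions and deaths.

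**2. The examples against the definitions.**

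| Event | Parenthesis in 10.3.2 | Other text |
|---|---|---|
| Unplanned admission for a sign or symptom of SBS | Not an AE, so not an SAE | 10.3.1: an untoward occurrence is an AE, and so is worsening of a concomitant illness, which Table 1 (footnote 3) says may be SBS-related. Criterion c: exempt only if elective and not worsened |
| Death from disease progression | Not an AE, so not an SAE | 10.3.2 a: death listed without exception. 10.3.3: an AE with a fatal outcome is reported as an SAE |

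Neither example has a basis in the definition to which the sentence refers.

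**3. Do other provisions close the gap?**
- Section 8.4.1 requires every AE to be recorded. That does not help if the event has been judged not to be an AE.
- The when-in-doubt rule in criterion c concerns whether a hospitalization occurred or was necessary, and it too starts from an AE.
- The AESIs in section 8.4.6 are neoplasms, suspected liver injury, pancreatitis and cholecystitis. Section 8.4.7 covers transmission of infectious agents, overdose, medication error and accidental exposure. Neither list includes dehydration or electrolyte disturbance.
- Section 10.3.3 asks for a causality assessment of each AE or SAE. An event never entered as an AE never gets one.

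**4. Which admissions are most exposed?** Dehydration and fluid or electrolyte disturbance, because section 2.2 ties dehydration to malabsorption and criterion 5 names severe water-electrolyte disturbance among SBS- or PS-related admissions.

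**5. Size of one omission.** Section 4.1 allows 6 to 16 treated patients, and section 9.2 plans 10. If one patient's only SAE is omitted, the reported incidence falls by 100/n percentage points:
- n = 16: 100/16 = 6.25
- n = 10: 100/10 = 10
- n = 6: 100/6 = 16.7

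**The case against.** The strongest reply is that the sentence is conditional. Its first half sends the reader to section 10.3.1, which has no disease carve-out, and the sentence after the parenthesis again defines an SAE as any untoward occurrence that meets a criterion. Other text also pushes towards reporting. Section 8.4.1 requires all AEs to be recorded, section 8.3.5 makes clinically relevant laboratory changes AEs, and criterion c treats complications during a hospital stay as AEs. A careful investigator would report these admissions. That stands, and it makes this a question of clarity rather than of a faulty rule. It does not explain why the examples are there or what they could correctly refer to.

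Harm from PS reduction is also watched by other means. Biochemistry, body weight and the PS regimen are checked at every visit. Section 7.1 makes deterioration, particularly in PS frequency and volume, a ground for stopping treatment. The internal Safety Committee works from several sources, "whether based on reported SAEs, review of all AEs and laboratory parameters reported". PS is not cut automatically at each visit either, since section 8.2.9 requires daily urine volume at least 10% above baseline. These points limit the harm. They do not restore an event missing from the AE and SAE tables.

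A reader might infer more than the documents support:
- **That sites are told never to report SBS admissions as SAEs.** The governing condition rules this out.
- **That catheter sepsis and bowel obstruction are equally exposed.** Section 2.2 describes catheter infection as a complication of PS, so it is not plainly a sign of SBS, and criterion 5 is eligibility wording that names PS-related events separately. A new obstruction is an untoward occurrence under 10.3.1.
- **That criterion 5 yields an expected number of lost events.** It caps past admissions at entry. Neither document gives an admission rate.

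**Conclusion.** The point holds as an internal inconsistency in the safety definitions. The two examples in section 10.3.2 conflict with section 10.3.1, with criteria a and c, and with the fatal-outcome rule in 10.3.3. A site that follows the examples could omit SBS-related admissions or deaths from both AE and SAE reporting, which would understate the treatment-emergent AE endpoint and the SAP's treatment-emergent SAE table.

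Each patient whose only SAE is omitted lowers the reported incidence by about 6 to 17 percentage points across the permitted 16 to 6 patients, and by 10 points at the planned 10. This assumes that the patient has no other reported SAE and that all treated patients form the denominator. How often it would happen cannot be estimated from the documents.

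This is a risk created by contradictory wording, not evidence that any event was omitted. The primary and key secondary efficacy analyses are unaffected. It still merits correction, because the text decides what enters the safety tables and the repair is small.

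**What to change.** Delete the parenthesis in protocol section 10.3.2, so that the sentence agrees with section 10.3.1 and criterion c. Add a statement that unplanned SBS- or PS-related hospitalizations, and deaths, are recorded as AEs and assessed against the SAE criteria. Keep only the exemption already in criterion c for elective treatment of a pre-existing condition that has not worsened. Send the site a short reminder when the amendment takes effect.

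The SAP needs no change, since its tables inherit the site's classification. The cost is one clause in an amendment, the reminder and a few more SAE reports to process.

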### a. Results in death

### b. Is life-threatening

The term 'life-threatening' in the definition of 'serious' refers to an event in which the patient was at risk of death at the time of the event. It does not refer to an event, which hypothetically might have caused death, if it were more severe.

# c. Requires inpatient hospitalization or prolongation of existing hospitalization

- In general, hospitalization signifies that the patient has been detained (usually involving at least an overnight stay) at the hospital or emergency ward for observation and/or treatment that would not have been appropriate in the physician's office or outpatient setting. Complications that occur during hospitalization are AEs. If a complication prolongs hospitalization or fulfills any other serious criteria, the event is serious. When in doubt as to whether "hospitalization" occurred or was necessary, the AE should be considered serious.
- Hospitalization for elective treatment of a pre-existing condition that did not worsen from baseline is not considered an AE.

### d. Results in persistent disability/incapacity

- The term disability means a substantial disruption of a person's ability to conduct normal life functions.
- This definition is not intended to include experiences of relatively minor medical significance such as uncomplicated headache, nausea, vomiting, diarrhea, influenza, and accidental trauma (e.g., sprained ankle) which may interfere with or prevent everyday life functions but do not constitute a substantial disruption.

# e. Is a congenital anomaly/birth defect

### f. Otherwise medically important:

- Medical or scientific judgment should be exercised in deciding whether SAE reporting
  is appropriate in other situations such as important medical events that may not be
  immediately life-threatening or result in death or hospitalization but may jeopardize the
  patient or may require medical or surgical intervention to prevent one of the other
  outcomes listed in the above definition. These events should usually be considered
  serious.
- Examples of such events include invasive or malignant cancers, intensive treatment in an emergency room or at home for allergic bronchospasm, blood dyscrasias or convulsions that do not result in hospitalization, or development of drug dependency or drug abuse.

# 10.3.3 Recording and Follow-Up of AE and/or SAE

# **AE and SAE Recording**

- When an AE/SAE occurs, it is the responsibility of the Investigator to review all documentation (e.g., hospital progress notes, laboratory reports, and diagnostics reports) related to the event.
- The Investigator will then record all relevant AE/SAE information in the eCRF.
- It is **not** acceptable for the Investigator to send photocopies of the patient's medical records to Pharmalex in lieu of completion of the AE/SAE eCRF page. All SAEs will be recorded and reported to Pharmalex immediately and under no circumstance should this exceed 24 hours. Sponsor is informed by Pharmalex.
- There may be instances when copies of medical records for certain cases are requested by Pharmalex. In this case, all patient identifiers, with the exception of the patient number, will be redacted on the copies of the medical records before submission to Pharmalex.
- The Investigator will attempt to establish a diagnosis of the event based on signs, symptoms, and/or other clinical information. Whenever possible, the diagnosis (not the individual signs/symptoms) will be documented as the AE/SAE.

# **Assessment of Severity**

The Investigator will assess severity for each event reported during the trial and assign it to one of the following categories:

- Mild: No or transient symptoms, no interference with the patient's daily activities.
- Moderate: Marked symptoms, moderate interference with the patient's daily activities.
- **Severe:** Considerable interference with the patient's daily activities, which the patient finds unacceptable. A severe reaction does not necessarily deem the AE as serious and an SAE are not always severe in nature.

# **Assessment of Causality**

- The Investigator is obligated to assess the relationship between trial intervention and each occurrence of each AE/SAE according to the following definitions:
  - o **Probably:** Good reason and sufficient documentation to assume a causal relationship.
  - o **Possibly:** A causal relationship is conceivable and cannot be dismissed.
  - o **Unlikely:** The event is most likely related to etiology other than the product.
  - o **Not related:** No relationship to product.
- The Investigator will use clinical judgment to determine the relationship.
- Alternative causes, such as underlying disease(s), concomitant therapy, and other risk factors, as well as the temporal relationship of the event to trial intervention administration will be considered and investigated.
- The Investigator will also consult the Investigator's Brochure in his assessment.
- For each AE/SAE, the Investigator **must** document in the medical notes that he/she has reviewed the AE/SAE and has provided an assessment of causality.
- There may be situations in which an SAE has occurred, and the Investigator has minimal information to include in the initial report to Pharmalex. However, it is very important that the Investigator always make an assessment of causality for every event before the initial transmission of the SAE data to Pharmalex.
- The Investigator may change his opinion of causality in light of follow-up information and send a SAE follow-up report with the updated causality assessment.
- The causality assessment is one of the criteria used when determining regulatory reporting requirements.

